### 3 SYNOPSIS

Study Title	Phase 1 Study of Treatment of Pain and Autonomic Dysreflexia by Deep Brain Stimulation in Participants with Spinal Cord Injury
Study Rationale	
Spinal cord injury (SCI) is a devastating disease, which exerts a disproportionate medical, social, and economic toll on society. Effective treatments are urgently needed for SCI, whether for immediate relief of symptoms or longer-lasting functional recovery. It (SCI) produces chronic loss of motor control, sensation and autonomic regulation below the level of the injury. Frequently disconnection is not total and some degree of below injury function remains. Unfortunately, the remaining functional connection can cause additional problems for patients (at least 20% of all SCI patients). In addition, dangerous rises in blood pressure can be produced by strong sensory input. This phenomenon is known as autonomic dysreflexia (AD). It occurs in 48% to 90% of patients with tetraplegia or high quadriplegia.
 
This study investigates the neurosurgical procedure of deep brain stimulation (DBS) in the midbrain’s periaqueductal and periventricular gray region (PAG/PVG). The use of DBS in PAG/PVG for drug-refractory non-metastatic chronic pain has been reported in the biomedical literature for at least several hundred patients, and continues to be used in many countries, including Germany and the United Kingdom. A small proportion of reported cases (about 21) of DBS applied at any brain site involved pain from spinal cord injury (SCI), and only 3 or 4 for the PAG/PVG. These reports, some of them from the 1970s, did not describe systematic studies. Extensive, modern pain testing was not done. The stimulation was not given time to work (it could require several weeks for effects to appear). The pathologies were in most cases inadequately characterized. Also, some preclinical evidence suggests PAG/PVG-DBS can also improve other SCI symptoms, such as motor deficits and autonomic dysreflexia (AD), which were never examined. The present study is designed to provide these missing details.
 
Thus, our study seeks to examine whether the safety and efficacy of prolonged DBS for SCI are sufficient to warrant its larger-scale study as therapy for pain and AD in SCI patients.

Trial Design	
 
• Controlled, open label, non-randomized, investigation in twelve (12) participants.
 
• Two sites: (1) Miami Veterans Affairs Medical Center; (2) University of Miami Miller School of Medicine.
 
• Informed Consent will be obtained prior to enrollment in the study.
 

Approximate Duration of Patient Participation	
 
• 52 weeks (±7 days) for each subject from Initial Visit until Final Visit.
 
• After implantation of the DBS device on the 8th week, scheduled safety and efficacy assessments will be performed at intervals of 4 weeks until study week 24, and at intervals of 8 weeks thereafter.
 

Approximate Duration of Study	

• End of Study is Defined as Last Subject’s Final Visit

• Total period of study is 36 months, from when 1st subject enrolled.

Study Objective(s)	
Primary: to determine whether Deep Brain Stimulation (DBS) applied bilaterally or unilaterally in the midbrain periaqueductal-periventricular gray (PAG/PVG) region provides acute or long-term relief of chronic SCI associated pain and autonomic dysreflexia.
 
Secondary: to assess the clinical effects of DBS on autonomic functioning; to determine with Aactiva PC+S whether local field potentials in the PAG/PVG can be used to predict the efficacy of DBS in this region

Diagnosis and Main Criteria for Inclusion	Major Inclusion Criteria:		
	Inclusion Criteria	Measure	Rationale
	Age $\geq$ 22	Years of age	Higher rates of neurological recovery if younger.
	Age $\leq$ 60	Years of age	Different injury patterns and higher risk of complications if older
	Level of injury at or above T12	Neurological exam	Eliminates injuries below thoracic level T12, which have different pain pattern
	1. Neuropathic pain at or below the level of injury, as determined based on pain in an area with neurological deficit and described as burning, shooting, electric, stinging etc.		
	2. The injury must have occurred at least 1 year prior to entering the study and participants must have experienced chronic pain for a minimum of six months.		
	3. The disability must have a grade of on the American Spinal Injury Association Impairment Scale (AIS) of ASIA-A, ASIA-B, ASIA-C or ASIA-D as determined by a qualified examiner.		
	4. Autonomic dysreflexia can be present but is not a necessary requirement. This is defined as a rise of systolic pressure by more than 30 mm Hg during noxious skin stimulation or when the bladder or bowel is full, or apparently spontaneously over a period of minutes.		
	5. Pain (neuropathic) of moderate severity or greater is present, when the patient is taking medication, with a score of at least 4 on a numerical rating scale (range of 0 to 10).		
6. Treatment with at least two of the following drug classes must have failed to give satisfactory pain relief within the last two years: anticonvulsants (e.g., pregabalin, gabapentin); antidepressants (e.g., trazodone, amitriptyline); NSAIDS (e.g., ibuprofen). In addition, at least one of the following must have proved ineffective: exercise-based rehabilitation, massage therapy using a variety of methods, acupuncture using pressure, needles, heat, or electrical stimulation on specific points on the body and psychological interventions such as cognitive therapy.			
7. Participants on medications for other conditions, such as diabetes, will be considered as candidates for this study. The dose will be monitored throughout the trial. (They will be excluded if the drug is being used to treat epilepsy, Parkinson's diseases, or other brain degenerative diseases.)			
8. The subject must be willing to comply with the protocol including all scheduled visits.			
9. Literate at 8th grade level or above.			
10. The subject must provide a letter of clearance for the DBS surgery from their primary physician.			

Main Criteria for Exclusion
	
Major Exclusion Criteria: Admission to study.
		
	Exclusion Criteria	Measure	Rationale
	Unable to give informed consent	Clinical examination	Protection of human subjects
	Prisoner or ward of the state	History	Vulnerable population
	Pregnancy	Urine or serum pregnancy test	Risk to fetus
	Prior history of abusing non-prescribed drugs	History	Vulnerable population
	Recent (one-year) history of alcohol abuse	History	Vulnerable population
	ASIA motor exam unobtainable	ASIA Motor Score	Baseline scoring needed for determination of change in score
	History of cardiac arrhythmia	History and ECG tracing	Higher risks of arrhythmia with DBS
	Renal disease, heart disease or uncontrolled hypertension, liver disease or hepatic cirrhosis	History	Highly variable rates of recovery
	Active major medical or psychiatric illness (MMSE<25)	History	Vulnerable population
	Significant post-traumatic encephalopathy from head trauma sustained at SCI	History	Vulnerable population
	Languages without local expertise	Family history	Lack of personnel or appropriate outcomes scales
	Pain is only nociceptive, due to muscle spasm	Physical examination	Neuropathic pain is therapeutic target
		
Major Exclusion Criteria: Treatment/Intervention procedure:
 
 
1. Coagulopathy requiring anticoagulation therapy
 
2. Thrombocytopenia or platelet dysfunction
 
3. Peripheral vascular disease
 
4. Comorbid neurological diseases or disorders, including a history of seizures
 
5. Active systemic infection or concurrent immunosuppressive therapy
 
6. Existing implantable cardiac pacemaker, defibrillator or neurostimulator
 
7. Requiring short-wave or microwave diathermy treatment during the course of the study.
 
8. Inability to cooperate
 
9. Any contraindication to MRI studies (All future MRIs, with the exception of brain MRIs, are excluded.)
 
10. Adverse reaction to stimulation (such as inability to stimulate at analgesic levels without causing clinical hypertension or hypotension) or allergy or hypersensitivity to any materials of the neurostimulation system
 
11. Depression, as defined by a Beck Depression Inventory (BDI-1a) score of 30 or above.
 
12. Subjects with any clinically significant abnormality, not expected on the basis of age (age-related), that is seen in magnetic resonance imaging (MRI).
 
	

Approximate Number of Patients
	
A maximum of 12 participants with incomplete or complete SCI and neuropathic pain at or below the level of injury.

Approximate Number of Study Centers
	
Two sites (VA Medical Center & University of Miami - Miller School of Medicine)


Concomitant Medication
	
Concomitant medications and treatments or procedures pertinent to the study treatment or to any adverse events will be recorded including:
 
 
1) name of drug, treatment, or description of procedure,
 
2) start and end dates and times, and
 
3) clinical indication and/or findings.
 
 
Investigational drugs and any other intervention (not part of the guidelines for management of SCI) known to have a potential impact on outcome will be prohibited.
 
Participants will be allowed to utilize over-the-counter drugs such as NSAIDs, acetaminophen and aspirin. Their use will be documented in the weekly pain assessments. A list of “allowed” medications will be provided to study participants. After the surgery, patients will be allowed to stay on the protocol if they take Tramadol (50-100 mg, 2 times a day for up to 2 weeks) as a rescue drug in addition to their stable medication.
 
The patient must be taking pain medication to maintain a stable level of medication from 4 weeks before surgery to 12 weeks after (the primary endpoint), except on the day of surgery. On the day of the surgery, in the presence of a physician who can provide immediate backup pain control if needed, medications will be stopped until the acute effects of DBS on analgesia have been evaluated.
 
On week 20 during a patient visit under medical supervision, patients will be instructed to take one fewer tablet or a smaller dose tablet, wait 4 hours and then see if their pain becomes worse. If it does become worse, they may take medication to reach the original dose. Subsequently, they may follow this procedure at home or during the following visits.

Study Intervention (Device Usage Protocol)
	

Device
	
The study will use PMA authorized, Class III, implantable, Neurostimulation Systems for Deep Brain Stimulation. The Medtronic Activa PC and PC+S DBS device systems will be used as designed without any modifications.

Study Intervention (Device Usage Protocol)	
Device Implant Procedure	
Participants presenting to the trial site with a history and mechanism consistent with chronic SCI with neuropathic pain below the level of injury, will be assessed using defined screening tests. Eligible participants will also undergo a multi-step consent process.
 
Upon successful consent, trained and certified study personnel will perform imaging and neurological systems exams. The neurological systems exams will be utilized as the baseline measure of neurological status including neuropathic pain and autonomic dysreflexia.
 
Upon successful completion of screening and baseline measurements, participants will undergo surgery to implant unilateral or bilateral DBS Leads (Model 3387S), extensions (Model # 37085 or 37086) and implantable neurostimulator (IFN) (Model 37601, or Model 37604).
 
After successful implantation and one week recovery, subjects will participate for 44 weeks in the study.

Treatment group	
Single treatment group. Ethical considerations forbid a control group that receives implant surgery without stimulation. Hence participants must serve as their own controls.

Frequency	
One-time implantation of Activa PC or Activa PC+S Deep Brain Stimulation device system. Continuous stimulation, or cycled in 12-hour on/off periods, or in shorter on/off periods, for ~ 40 weeks. Voltage range 0.1-10V.

Safety Evaluation	
 
1) Although preclinical data and clinical experience suggests DBS and device implantation is relatively safe, several adverse events are possible and will be noted,
 
2) Comprehensive pain, motor and autonomic assessment will occur on screening and enrollment (baseline) and then at every on-site visit week throughout the study.
 
3) The correct functioning of the DBS apparatus will be monitored at 4-week intervals after implantation until study week 24, and at 8-week intervals thereafter.
 
4) Pain Assessments using the ISCI-PDS:B will evaluate development of neuropathic pain syndromes.
 

Secondary outcomes	
 
1) Tilt table response exam
 
2) Autonomic Standards Assessment (BP, HR, sympathetic skin response)
 

Safety Analysis Plan	
Primary Safety Analysis	
The analyses for safety will focus on changes in reported pain intensity during routine patient visits. All AEs and SAEs will be listed and their incidence compared to historical controls. The primary endpoint analyses will occur at 44 weeks post-implantation.

Secondary Outcomes and Analyses	
The secondary hypothesis concerns autonomic assessment that will also take place during routine patient visits. Heart rate, blood pressure, sweating, body temperature and breathing will also be classified as normal, abnormal, unknown or not obtainable. Lower urinary tract, bowel and sexual function will also be scored.
 
Comprehensive testing sessions will analyze vagal and sympathetic influences on the cardiovascular system, measuring blood pressure and heart rate variability (power spectrum analysis) during sit-up or tilt-table challenge.
 
Assessment of motor and non-pain somatosensory function will be done during visits every 4 weeks. Clinical sensory testing will include Light Touch and Pin Prick tests defined in the ASIA standards [1]. The Beck Depression Inventory (BDI-1a) will also be used, to assess emotional function in neuropathic pain [4]. If BDI assessment (>30) suggests suicidal thoughts, the Columbia Suicide Severity Rating Scale will be used in consultation with a clinical psychologist.

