Autonomic functioning after SCI depends on the injury level. Visceral efferents are damaged directly by mid-thoracic or sacral injuries. Higher control of autonomic function is degraded after cervical or high thoracic SCI, when only vagal control remains. Autonomic dysreflexia (AD) is a frequent consequence of cervical or high thoracic injuries. It mostly occurs when the lesion is above the 6th thoracic segment. Its estimated frequency is 48-90% in patients with tetraplegia or high quadriplegia [24-26]. AD is a cluster of symptoms caused by a massive sympathetic outflow, which includes elevated blood pressure, headache, flushing, sweating above the lesion level and abnormal heart rhythms. It is typically provoked by activity in visceral or cutaneous afferents below the injury. Distension of bladder or colon, such as occurs from loss of control of evacuation, may precipitate AD. It can occur sporadically, triggered several times each day, but sometimes it lasts for many days, since the patient is generally unaware of aggravating stimuli below the injury level.

Various categories of antihypertensive agents are used for symptomatic control of AD, in particular nitrates (e.g., topical nitroglycerin), calcium blockers (e.g., nifedipine) and selective alpha-adrenergic antagonists (e.g., prazosin, terazosin) [27]. In the short-term, these treatments are generally adequate. However, because AD can present as an acute crisis, long-term treatment with an effective blocking dose is poorly matched to the breakthrough of symptoms and their chronic sequelae. Alpha-adrenergics, for example, in addition to their adverse acute effects and contraindications, produce receptor upregulation with long-term use. Additional problems are specific to SCI. Norepinephrine facilitates movement generation in the spinal cord and is a transmitter at sphincter muscles of hollow organs. Blockade of its principal alpha-1 receptors can therefore exacerbate functional deficits in SCI.

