## 11 STUDY OBJECTIVES AND PURPOSE

### 11.1 Purpose/Objective

We propose an investigation of the safety of deep brain stimulation (DBS) for the alleviation of chronic neuropathic pain in patients with spinal cord injury (SCI). The stimulation will be applied bilaterally or unilaterally in the midbrain periaqueductal-periventricular gray region (PAG/PVG). Indications of efficacy will also be examined. Patients will receive bilateral implants in the case of complete SCI (ASIA-A). Patients with an incomplete SCI who can localize pain to one side of the body will receive unilateral stimulation of the PAG contralateral to the sites of pain.

Although PAG/PVG stimulation has been used previously in SCI pain patients, the small numbers of patients studied and the lack of detail on their testing and injury status makes a phase I trial appropriate. Effective treatment of pain could also bring benefits to patients with autonomic dysreflexia (AD), which can be provoked by painful visceral and somatic stimuli below an incomplete lesion. Autonomic functioning will therefore be studied as a secondary outcome. Preclinical evidence from rats suggests that prolonged PAG stimulation may lead to enduring improvements in all deficits (sensory, motor, and autonomic). The proposed study will therefore examine if such improvements occur when PAG/PVG stimulation is applied over many weeks.

Aim 1 is to determine whether DBS in the PAG/PVG at analgesic intensities produces any systemic or neurological adverse effects in patients with longstanding SCI (>1 year), either immediately or as a result of prolonged application for up to 40 weeks.

Aim 2 is to determine whether acute application of DBS in the PAG/PVG influences the severity of spontaneous ongoing pain caused by longstanding SCI.

Aim 3 is to determine whether DBS in the PAG/PVG affects stimulus-evoked or persistent hypertension (a major sign of autonomic dysreflexia) in chronic SCI patients.

Aim 4 is to determine whether prolonged PAG/PVG stimulation (for 10 months) leads to cumulative changes in chronic pain severity, motor or autonomic symptoms in chronic SCI patients.

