### 13.3 Inclusion Criteria

- a) Age: 22 - 60 years old at last birthday;
- b) Diagnosis of traumatic SCI at or above the 12th thoracic segment (T12) that occurred >365 days;
- c) Neuropathic pain below the level of injury, as determined based on pain in an area with neurological deficit and described as burning, shooting, electric, stinging etc.

- d) The injury must have occurred at least 1 year prior to entering the study and participants must have experienced chronic pain for a minimum of six months.
- e) The disability must have a grade on the American Spinal Injury Association Impairment Scale (AIS) of ASIA-A, ASIA-B, ASIA-C or ASIA-D as determined by qualified examiners.
- f) Pain (neuropathic) of moderate severity or greater is present, when the patient is taking their routine pain medication, with a score of at least 4 on a numerical rating scale (range of 0 to 10).
- g) Participants who are on medications for other conditions, such as diabetes, will be considered as candidates for this study. The dose will be monitored throughout the trial. (They will be excluded if the drug is being used to treat epilepsy, Parkinson's diseases, or other brain degenerative diseases.)
- h) Participants will be allowed to utilize over-the-counter drugs such as NSAIDs, acetaminophen and aspirin. Their use will be documented in the weekly pain assessments. A list of "allowed" medications will be provided to study participants. After the surgery, patients will be allowed to take stay on the protocol if they take Tramadol (50-100 mg, 2 times a day for up to 2 weeks) as a rescue drug in addition to their stable medication.
- i) The patient must be taking pain medication to maintain a stable level of medication from 4 weeks before surgery to 12 weeks after (the primary endpoint), except on the day of surgery. On the day of the surgery, in the presence of a physician who can provide immediate backup pain control if needed, medications will be stopped until the acute effects of DBS on analgesia have been evaluated.
- j) The participant must be willing to comply with the protocol including all scheduled visits.
- k) Autonomic dysreflexia can be present but is not a necessary requirement. Autonomic dysreflexia will be defined as rise of systolic pressure by more than 30 mm Hg during noxious skin stimulation or when the bladder or bowel are full, or apparently spontaneously over a period of minutes
- l) Literate at 8th grade level or above.

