#### **14.6 Medication(s)/Treatment(s) Permitted (Concomitant Medications) and not Permitted Before and/or During the Trial:**

##### A. Permitted Treatment

All medication taken by the participant during the study is to be recorded. All medications required to treat the participant should be administered as recommended. The following data will be recorded for all included participants up to the end of the study period: name of drug or nature of treatment, start and end dates, hours of administration, and indication. Fluid and blood replacement will be measured and documented on a daily basis. Additionally, any therapeutic or surgical procedure performed during the study period should be recorded, including the date, description of the procedure, and clinical findings

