In addition to the continual monitoring of adverse events, safety analyses will use generalized linear models. The main dependent variable of interest is the Numeric Rating Scale (NRS) score for pain. Additionally there will be a fairly large number of dependent variables derived from assessments of other symptoms. Distributions will be modeled as binomial (yes=1 or no=0) or multinomial (e.g., score =1, 2, or 0) or normal (e.g., heart rate peak power after tilt, quantitative sensory thresholds). Less frequently, a Poisson distribution will be appropriate (e.g., number of times the patient reports autonomic dysreflexia in a given period). An appropriate link function will be chosen for each assumed distribution. Covariates to be considered are injury level, injury completeness and electrode configuration. The hypotheses to be tested for any variable (using the above factor coding) is that  $B \succ A$ ,  $C \succ B$ ,  $D \succ B$  and  $D \succ C$ . Marginal means can be used for this (except in multinomial examples, when main effects must suffice). Some participants may lack data from one condition (if they immediately opted for continuous high-level stimulation after the initial untreated period). If the continuous treatment is stopped soon after it starts, only the placebo effect ( $A \succ B$ ) will be available. Representative independent variables from each type of symptom will be further explored by discriminant analysis, which can confirm that one or more treatment condition represents a distinct state in the multivariate outcome space.

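### Blood-pressure drugs are recorded but enter no analysis, so the long-term autonomic results can be confounded by drug changes in either direction

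*Combined protocol and SAP*

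**What the plan says.** **Stability.** The synopsis (Concomitant Medication) and section 13.3(i) carry one rule: "The patient must be taking pain medication to maintain a stable level of medication from 4 weeks before surgery to 12 weeks after". It names pain medication only. Surgery falls in study weeks 7 and 8 (section 12.6.1), so the window closes at about week 20.

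**Other drugs.** Section 13.3(g) admits participants taking drugs for other conditions and adds: "The dose will be monitored throughout the trial". Section 14.6 B prohibits investigational drugs and outcome-relevant interventions that lie outside the guidelines for SCI management. Section 7.1 states: "Various categories of antihypertensive agents are used for symptomatic control of AD". It gives nitrates, calcium blockers and alpha-adrenergic antagonists as examples.

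**Recording.** Section 14.6 A says: "All medication taken by the participant during the study is to be recorded". The fields are: "name of drug or nature of treatment, start and end dates, hours of administration, and indication". Table 2 schedules a medication diary 50 times. The synopsis limits recording to medication pertinent to the study treatment or to adverse events.

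**Outcomes.** Aim 3 asks whether stimulation "affects stimulus-evoked or persistent hypertension (a major sign of autonomic dysreflexia) in chronic SCI patients". Aim 4 asks about cumulative change, including in autonomic symptoms, over 10 months. Section 16 lists blood pressure, heart rate, tilt response and sympathetic skin response among the efficacy parameters. Section 17.1 gives as an example of a Poisson outcome the "number of times the patient reports autonomic dysreflexia in a given period".

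**Analysis.** The covariates to be considered in section 17.1 are injury level, injury completeness and electrode configuration. Section 16 has no medication-use outcome, although the extension (section 12.6.1) does assess medication usage.

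**The concern.** Participants serve as their own controls (section 12.3), and section 12.5 states that no specific measures against bias are taken. A long-term autonomic result is then a comparison of follow-up with the pre-implant state, and anything else that changed over that time is mixed with stimulation.

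Blood-pressure drugs are an obvious candidate. If one is added or raised after an AD crisis, later pressures and AD counts may fall without any effect of stimulation. If stimulation helps and a drug is withdrawn, pressure may look unchanged and the benefit is missed. Pain is protected by a stability rule for part of follow-up. The autonomic outcomes have no such rule, and no analysis stands in for one.

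The synopsis places relief of AD in the primary objective, and AD is in the study title. Sections 11.1 and 11.4 treat autonomic function as secondary.

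**Working it through.** The documents give no figure for blood-pressure drug use, for the size of a drug effect, or for the variability of blood pressure. There is therefore no figure to reproduce. The check is first textual, then an illustration on stated assumptions.

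**1. Is there any hold on blood-pressure drugs?** The stability rule covers pain drugs only. The prohibition spares SCI-guideline treatment, and section 7.1 describes antihypertensives as used for AD. Drugs for other conditions are monitored, which is not the same as held. So changes are permitted.

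**2. Does any analysis use the changes?** The covariate list in 17.1, the efficacy parameters in 16 and the description in 17.2 contain no medication term, rule or outcome. So they are not used.

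**3. Could the records support an analysis?** Largely. Drug, dates, hours and indication are to be recorded, and the diary is frequent. Neither field list (synopsis, 14.6 A) includes dose, although 13.3(g) says dose is monitored. The synopsis says pertinent medication and 14.6 A says all medication. An increase or reduction at constant drug cannot be coded from start and end dates alone.

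**4. Which results are exposed?** Section 15 lists on-site visits at weeks 12, 16, 20, 24, 32, 40, 48 and 52. Five of these eight (24 to 52) fall after week 20, as do two of the three post-implant tilt examinations (weeks 32 and 52 of 20, 32 and 52). Blood-pressure drugs are free of any rule at all eight. By contrast, the cuff measurement before and during stimulation (section 12.3, repeated at week 12) compares off with on within one session, where a drug change made over weeks largely cancels.

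**5. Size, on assumed values.** Let k of 12 participants start or raise a drug that lowers systolic pressure by d mm Hg, with no stimulation effect. Shift in mean change = k × d / 12.

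- k = 1, d = 5: 5/12 = 0.4 mm Hg
- k = 1, d = 20: 20/12 = 1.7 mm Hg
- k = 4, d = 10: 40/12 = 3.3 mm Hg
- k = 6, d = 20: 120/12 = 10 mm Hg

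AD is not required for entry, so the number with AD may be below 12. If 4 to 8 had it (an assumption) and one of them gained a 20 mm Hg drug effect, the mean among them would move by 20/8 = 2.5 to 20/4 = 5 mm Hg.

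One participant reclassified moves a proportion by 1/12 = 8.3 points, or by 12.5 to 25 points with a denominator of 8 to 4.

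**6. Chance of a spurious nominal benefit.** This is a simulated paired t-test with n = 12, two-sided 5% level, no stimulation effect and 40,000 runs per case. The SD of change is assumed.

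| k | d (mm Hg) | SD 8 | SD 12 | SD 16 |
|---|---|---|---|---|
| 0 | – | 2.4–2.6% | 2.4% | 2.4% |
| 2 | 10 | 6.6% | 5.3% | 4.6% |
| 4 | 10 | 16.7% | 11.1% | 8.4% |
| 2 | 20 | 8.5% | 7.8% | 6.6% |
| 4 | 20 | 31.8% | 22.3% | 16.7% |

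Section 17.3 proposes descriptive analysis only, so the table shows how far a summary could mislead. It is not the error rate of a planned test.

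**The case against.** The strongest reply has four parts.

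- **The drugs are not out of sight.** Medication is recorded, the diary is scheduled 50 times, and dose is said to be monitored. This stands. A reader might infer that these drugs can change unnoticed and that a reduction would be invisible, but the documents do not support that. The gap is only that no analysis uses the records.
- **Aim 3 has a comparison that resists this bias.** The within-session off/on measurement, and the possible brief inactivations at programming visits (section 12.5, Table 2), are little affected by slow drug changes. This also stands, and it confines the point to Aim 4 and the long-term part of Aim 3.
- **The plan is descriptive.** It sets no success rule for AD, and its covariates are ones to be considered rather than a closed list. True, but a descriptive before-after summary is confounded in the same way, and 17.1 does go on to specify models and hypotheses.
- **The sizes are assumed.** They are. In addition, AD is defined in 13.3(k) by a rise of more than 30 mm Hg. A drug that lowers the pressure level need not lower the rise by the same amount.

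A further inference should be resisted. The exclusion reads "Renal disease, heart disease or uncontrolled hypertension, liver disease or hepatic cirrhosis", and one might conclude that nobody enrolled could show relief of hypertension by blood-pressure value. That does not follow. Section 13.3(k) expressly admits participants with AD, including apparently spontaneous rises, and a controlled pressure can still fall.

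**Conclusion.** The point holds for the baseline-to-follow-up autonomic results: Autonomic Standards blood pressure, tilt response and AD counts. Blood-pressure drugs may change, the changes are recorded, and no analysis uses them. The bias can run in either direction.

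Its size cannot be known from the documents. On the assumptions shown, the shift in mean systolic change is 0.4 to 10 mm Hg. It depends on the number of participants who change drugs, the drug effect, and the number with AD. If no participant changes a blood-pressure drug, the bias is zero, and the proposed table would show that.

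The documents do not support the stronger reading that the plan would declare stimulation effective for AD on the strength of a drug effect. No decision rule exists, autonomic function is secondary in sections 11.1 and 11.4, and the acute comparison is largely protected. This is a cheap and worthwhile improvement. It is not a flaw that undermines the trial.

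**What to change.** 1. In 17.1 and 17.2, define a list of blood-pressure-active drugs. At each autonomic visit, code their use as unchanged, added/increased or reduced/stopped against the pre-implant state, using the medication records and diary.
2. Reconcile the synopsis (Concomitant Medication), 13.3(g) and 14.6 A so that every such drug is captured with its dose.
3. Report the long-term blood-pressure and AD results by this code.
4. Prespecify two sensitivity analyses: (a) only participants with unchanged drugs; (b) a drug added or increased for AD or blood pressure counted as not improved. Rule (b) should stay a sensitivity analysis, because as the main rule it could hide a real benefit.
5. Report change in antihypertensive use as an outcome beside these results, so that unchanged pressure on less drug is visible.

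The cost is one dose field, a small amount of coding for 12 participants and a few lines of analysis text. The AD result may look less favourable. Patients' drug care, eligibility and the wording of Aim 3 stay as they are.
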